**Notes:**

1. Treatment is given every other day.
2. Completed at least 2 weeks prior to treatment with Lattice SBRT.
3. Every patient will be required to have 1 on-treatment visit per standard clinical practice.
4. For women of child-bearing potential only, and within 20 days prior to study entry.
5. +/- 1 week.
6. +/- 2 weeks
7. Within the past 4 months
8. Imaging will be performed per care team. CT, MRI, or PET/CT are acceptable modalities, but it is recommended that the same method be used at all imaging timepoints.
9. Follow up will take place at 90 days, 180 days, and 360 days, +/- 4 weeks.
10. PROMIS and PRO-CTCAE will be utilized at these timepoints.
11. AEs will be tracked through 360 days post treatment.
12. Peripheral blood for immune monitoring can be collected up to 2 weeks prior to first day of treatment, but no later than 1st day of treatment.
13. Peripheral blood for immune monitoring will be collected at fraction 5 only.
14. For all patients, assessments of hematologic and metabolic function will be collected no more than 1 week before treatment (including on the day of treatment), immediately after radiotherapy completion (Fraction 5), at 48-72 hours after radiotherapy completion, and 7 days (+/- 1 day) after radiotherapy completion. This must include assessments of uric acid, potassium, phosphorus, and calcium.

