## **5.8 Definitions of Evaluability**

All patients enrolled on the study are evaluable for toxicity if they have received at least one fraction of radiation. Patients are evaluated from first receiving study treatment until 90 days after the conclusion of treatment or death. Participants who are consented but do not receive study treatment will be replaced.

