## **5.11 Duration of Therapy**

If at any time the constraints of this protocol are considered to be detrimental to the patient's health and/or the patient no longer wishes to continue protocol therapy, the protocol therapy should be discontinued and the reason(s) for discontinuation documented in the case report forms.

In the absence of treatment delays due to adverse events, treatment may continue for a maximum of 2 weeks or until one of the following criteria applies:

- Documented and confirmed disease progression

- Death
- Adverse event(s) that, in the judgment of the investigator, may cause severe or permanent harm or which rule out continuation of study drug
- General or specific changes in the patient's condition render the patient unable to receive further treatment in the judgment of the investigator
- Suspected pregnancy
- Serious non-compliance with the study protocol
- Lost to follow-up
- Patient withdraws consent
- Investigator removes the patient from study
- The Siteman Cancer Center decides to close the study

Patients who prematurely discontinue treatment for any reason will still be followed as indicated in the study calendar.

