## 9.0 DATA SUBMISSION SCHEDULE

Case report forms with appropriate source documentation will be completed according to the schedule listed in this section.

Case Report Form	Submission Schedule
Original Consent Form	Prior to registration
On-Study Form Medical History Form	Prior to starting treatment
Specimen Collection Form	Screening, immediately after radiotherapy completion (Fraction 5), 14 days after radiotherapy, and 30 days after radiotherapy
Questionnaires	Baseline, after radiation at 2 weeks, 1 month, 3 months, 6 months, and 1 year
Toxicity Form	Continuous
Treatment Summary Form	Completion of treatment
RECIST Form	Baseline, then 3 months, 6 months, and 1 year post treatment
Follow Up Form	After radiation at 2 weeks, 1 month, 3 months, 6 months, and 1 year
Death Form	At time of death (if applicable)

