### 11.2 Study Endpoints

The co-primary endpoints are rate of local control of the treated (i.e. target) lesion at 6 months, and proportion of patients with treatment related grade 3+ CTCAE v5.0 toxicity. Local control will be determined by RECIST 1.1 analysis of baseline compared with imaging at 6 months. Imaging may include CT scan, PET/CT, or MRI. It is strongly suggested that the same imaging modality is used between baseline and at every follow-up timepoint for staging of disease.

Importantly, there are limited available data to determine expected local control of large tumors after SBRT. Almost all studies have focused on tumors with average maximal diameter of only 5.5 cm corresponding to a tumor volume of approximately 87 cc. In such studies, local control rates are approximately 70-85%. In the pilot study of Lattice SBRT at Washington University, the median treated tumor volume was 435 cc (N=14). Likewise, these few studies of SBRT for large tumors report a grade 3+ toxicity rate of 5-25%, varying based on tumor location.

Due to the lack of a reliable historical comparison, the enrollment target was defined by clinical considerations as opposed to power calculations for comparison with a historical control. This study instead seeks to establish the expected local control rate at 6 months for patients with such large tumors treated with Lattice SBRT. After discussing with internal and external stakeholders, we determined that a clinically reasonable bound on local control at 6 months would be 15%. Approximately 47 patients would be required to determine local control with a 95% confidence interval of +/- 15%; 67 patients will be enrolled to get 47 evaluable patients. We anticipate that up to 30% of patients may not be evaluable for local control at 6 months and are accounting for this potential drop-out rate by enrolling 67 patients. This is because patients with very large tumors needing palliative radiotherapy often have short survival.

Likewise, the study seeks to establish the expected grade 3+ treatment related toxicity rate for treatment of large tumors with lattice SBRT. The treatment will be considered safe if the grade 3+ treatment related toxicity rate is less than 20%, which is in line with prior studies of SBRT of large tumors.

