### **11.3 Data Analysis**

Demographic and clinical characteristics including treatment toxicity will be summarized using descriptive statistics. RECIST 1.1 will be used to determine local control per the protocol described in Appendix E. The RCI will be used to compare the QoL scores between before and after treatment with Lattice SBRT.

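### Sections 11.2 and 11.3 give two different reading rules for 6-month local control, and documented 3-month progression without a 6-month scan is not assigned to failure

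*Combined protocol and SAP*

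**What the plan says.** Section 11.2 names local control of the treated lesion at 6 months as a co-primary endpoint and says how it is read: "Local control will be determined by RECIST 1.1 analysis of baseline compared with imaging at 6 months". It then plans for attrition: "We anticipate that up to 30% of patients may not be evaluable for local control at 6 months". The reason given is survival: "This is because patients with very large tumors needing palliative radiotherapy often have short survival". Section 11.4 puts the unevaluable share at 20-30% and relies on at least 47 evaluable patients out of 67. The Protocol Summary also sets 47 evaluable as the goal.

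Section 11.3 gives the analysis rule: "RECIST 1.1 will be used to determine local control per the protocol described in Appendix E". In Appendix E, progression of target lesions is a rise of at least 20% and at least 5 mm from the smallest sum recorded on study. A note adds that a new lesion is also progression.

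On timing, Section 9.0 makes the RECIST form due as follows: "Baseline, then 3 months, 6 months, and 1 year post treatment". The notes to the Schedule of Activities set the visits: "Follow up will take place at 90 days, 180 days, and 360 days, +/- 4 weeks".

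On evaluability, Section 5.8 says: "All patients enrolled on the study are evaluable for toxicity if they have received at least one fraction of radiation". There is no matching definition for local control. Section 5.13 treats an unreachable patient as withdrawn but does not say what this does to the rate.

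**The concern.** The trial has one arm, no comparison with a historical control and no pass mark for local control. Its efficacy result is the estimated rate itself, so the rule that produces the rate should leave nothing to choose after the data are in. Two things are left open.

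- **Reference and scope.** A baseline-to-6-month comparison and a smallest-sum rule can disagree whenever a tumour shrinks by 3 months and then regrows. The new-lesion note in Appendix E also has no exception for disease outside the treated target, although Section 11.2 is about the treated lesion only.
- **Early failures.** The 3-month reading is collected, so some local failures will be on file by then. If such a patient dies or misses the 6-month scan, the literal text of Section 11.2 provides no comparison and the patient leaves the rate. A known failure is then discarded, which overstates control among patients whose outcome is known.

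Enrolling 67 patients protects the width of the interval. It does not settle either question.

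**Working it through.** **The plan's own figures.** Inputs from Sections 11.2 and 11.4: a 95% interval of +/- 15 points, 47 evaluable, 67 enrolled, 20-30% unevaluable.

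- The exact (Clopper-Pearson) half-width near a rate of 50% is 0.1510 at n = 46 and 0.1493 at n = 47, so 47 reproduces.
- 47 / 0.70 = 67.1, in line with 67 enrolled.
- 67 x 0.70 = 46.9 and 67 x 0.80 = 53.6, so about 47 to 54 evaluable and 13 to 20 not.

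The sample size needs no change.

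**Reference conflict.** Take sums of 10.0 cm at baseline, 7.0 cm at 3 months and 8.6 cm at 6 months (invented values that respect the visit schedule).

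- Against baseline, as in Section 11.2: 8.6 / 10.0 - 1 = -14%, not progression.
- Against the smallest sum, as in Appendix E: 8.6 / 7.0 - 1 = +22.9%, and 8.6 - 7.0 = 1.6 cm = 16 mm. Both thresholds (20% and 5 mm) are passed, so this is progression.

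Each patient reclassified in this way moves the rate by 1/47 = 2.1 points or 1/54 = 1.9 points. The documents give no basis for guessing how many there will be.

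**New lesions.** If the treated mass has shrunk and a new lesion appears elsewhere, Section 11.2 reads local control and the Appendix E note reads progression.

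**Early failures without a 6-month scan.** Let x be the number controlled among n patients with a 6-month scan, and k the number with recorded 3-month target-lesion progression and no 6-month scan. The literal Section 11.2 rate is x/n. With the known failures kept, it is x/(n + k). The documents give no early local failure rate, so x and k are assumptions. In each case k is set near the failure share seen among scanned patients: 9/47 x 20 = 3.8 and 10/54 x 13 = 2.4.

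| Evaluable | k | x/n | x/(n + k) | Difference |
|---|---|---|---|---|
| 47 | 4 | 38/47 = 80.9% | 38/51 = 74.5% | about 6 points |
| 54 | 2 | 44/54 = 81.5% | 44/56 = 78.6% | about 3 points |
| either | 0 | x/n | x/n | 0 |

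**All-treated view, for context.** Suppose all patients without a 6-month scan died before it and none is censored. One minus the cumulative incidence of local failure over all 67 is then 1 - 13/67 = 80.6% in the first case and 1 - 12/67 = 82.1% in the second. With k = 0 these become 1 - 9/67 = 86.6% and 1 - 10/67 = 85.1%.

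**Visit window.** 180 - 28 = day 152 to 180 + 28 = day 208.

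**The case against.** The strongest reply is that the plan is clearer than it looks. Naming RECIST 1.1 in Section 11.2 may only identify the scans, while Section 11.3, the data-analysis section, makes Appendix E operative with an explicit smallest-sum rule. Early death is not ignored either: the Protocol Summary and Sections 11.2 and 11.4 all point to an evaluable-only proportion with patients who die early outside the denominator. No decision threshold hangs on the result.

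Much of this stands. A reader might infer that the documents say nothing about death; they do not support that, because the exclusion is implied. It appears only as sample-size reasoning, however, and it does not settle a patient who progresses locally at 3 months and then dies. On the reference, the Section 11.2 sentence still names baseline and 6 months as the comparison, so two careful analysts could differ.

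A reader might also be tempted by larger numbers. Counting every unevaluable patient as not controlled gives 38/67 = 56.7% or 44/67 = 65.7%, but no section suggests an alive-and-controlled rate over all 67. The best-to-worst range of 20/67 = 29.9 or 13/67 = 19.4 points is simply the missing fraction.

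Nor can one infer that the evaluable-only rate is too high for all treated patients. In the illustration the competing-risk figure is close to the scans-only one (80.6% against 80.9%, and 82.1% against 81.5%), and it is higher when k = 0. The direction of that selection is unknown.

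**Conclusion.** The point holds in limited form. Sections 11.2 and 11.3 (through Appendix E) can class one patient in opposite ways, and the plan gives no formal rule for who is evaluable for local control. The literal wording of Section 11.2 would drop recorded 3-month local failures that have no 6-month scan.

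Under the assumed counts, the two readings that the text supports differ by about 3 to 6 points. That is inside the planned +/- 15 and vanishes if there are no such patients. The effect of the reference conflict comes on top and cannot be sized from the documents. This is an ambiguity in a co-primary endpoint that should be closed before analysis. It is not a demonstrated bias and does not affect the sample size.

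**What to change.** Amend Sections 11.2 and 11.3 as follows.

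1. Use one reference for the treated lesion or lesions, the Appendix E smallest sum on study. State that new lesions outside the treated target do not count as local failure.
2. Count target-lesion progression at any scan up to and including the 6-month visit window (days 152 to 208) as failure, even without a 6-month scan.
3. Define evaluable for local control as having documented target-lesion progression by then or a 6-month scan. Report how many patients are excluded for death and how many for a missing scan.
4. As sensitivity analyses in all treated patients, report the cumulative incidence of local failure with death as a competing event, the proportion alive and locally controlled at 6 months, and best- and worst-case bounds.

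The competing-risk estimate belongs among the sensitivity analyses. It counts death without documented local failure as failure-free, which is debatable as the main estimate when survival is short. Item 4 is still needed, because item 3 keeps early failures while leaving out early deaths without failure, and so can sit below the all-treated figure (74.5% against 80.6% in the first illustration).

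The cost is wording and slightly more analysis, and the headline rate may come out somewhat lower. No new visits or patients are needed: the 3-month RECIST form and the Death Form are already collected, and Section 5.11 keeps early stoppers in follow-up: "Patients who prematurely discontinue treatment for any reason will still be followed as indicated in the study calendar".

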Study Population:	67 adult patients will be enrolled and treated, (with a goal of 47 evaluable patients), $\geq 18$ years of age with ECOG $\leq 2$ . At least 10 patients will be enrolled in each cohort (soft tissue sarcomas, thoracic cancers (including esophageal), abdominal, and pelvic cancers). All genders and races will be included. Any participants who do not receive treatment will be replaced.
Phase:	N/A
Description of Sites / Facilities Enrolling:	This is a single-institutional study conducted at Washington University School of Medicine
Description of Study Intervention:	5-fraction Lattice SBRT delivered to 20 Gy with a simultaneous integrated boost (SIB) to 66.7 Gy.
Study Duration:	16 months plus 2 weeks for treatment and 12 months follow up
Participant Duration:	2 weeks of treatment plus 12 months follow up.

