### **11.6 Continuous Toxicity Monitoring using Pocock-type boundary**

The toxicities will be reviewed and monitored on a continuous basis. Early stopping of this trial will be based on the excessive Lattice SBRT treatment emergent severe adverse events (TSAE) of grade 3 or higher non-hematological rate. We assume the TSAE rate is expected ~30% or less and a toxicity rate of 40% or more is not desired. Sequential boundaries will be used to monitor dose-limiting toxicity rate after three patients are enrolled and evaluable for toxicity. The accrual will be halted if excessive numbers of TSAE are seen, that is, if the number of TSAE is equal to or exceeds  $b_n$  out of  $n$  patients with full follow-up (see table below). This is a Pocock-type stopping boundary that yields the probability of crossing the boundary at most 0.3 when the rate of TSAE is equal to the acceptable rate of 0.3 (Ivanova, Qaqish, and Schell 2005).

number of patients	3	4	5	6	7	8	9	10	11	12	13	14	15	16	17	18	19	20	21	22
Boundary (bn)	3	3	4	4	5	5	6	6	7	7	7	8	9	9	9	9	9	10	10	
number of patients	23	24	25	26	27	28	29	30	31	32	33	34	35	36	37	38	39	40	41	42
Boundary (bn)	10	11	11	11	12	12	12	13	13	13	14	14	14	15	15	15	16	16	17	17
number of patients	43	44	45	46	47	48	49	50	51	52	53	54	55	56	57	58	59	60	61	62
Boundary (bn)	17	18	18	18	19	19	19	20	20	20	21	21	21	22	22	22	23	23	23	24
number of patients	63	64	65	66	67															
Boundary (bn)	24	24	25	25	25															

Thus, based on the continuous monitoring algorithm for toxicity using Pocock-type boundary, the study will halt if excessive Lattice SBRT -related adverse events occur in the 3 of the first 3 patients, or 4 of the first 6, or 5 of the first 9, or 5 of the 10 patients has completed the trial.

The operating characteristics including early stopping probability, expected number of TSAsEs and associated with the calculated boundaries are listed below.

TEAE rate	Early stopping (hitting the boundary) probability	Expected number of TEAEs	Standard deviation on number of TEAEs	Expected number of patients enrolled	Standard deviation of number of patients enrolled	Expected TEAE rate	Standard deviation on TEAE rate
0.30	0.3980	14.08	6.93	46.94	26.85	0.41	0.23
0.40	0.8648	9.76	7.27	24.38	22.99	0.56	0.22
0.50	0.9950	5.63	4.22	11.26	11.69	0.66	0.22
0.60	1.0000	3.85	2.24	6.41	5.76	0.75	0.21
0.70	1.0000	3.03	1.36	4.32	3.28	0.82	0.19
0.80	1.0000	2.56	0.88	3.20	1.98	0.89	0.15
0.90	1.0000	2.24	0.53	2.49	1.11	0.95	0.11

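### The 20% safety criterion carries no interval or error rate: a true severe-toxicity rate of 20% meets it about half the time, and one of 25% meets it 18% of the time

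*Combined protocol and SAP*

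**What the plan says.** Section 11.2 names as co-primary the "proportion of patients with treatment related grade 3+ CTCAE v5.0 toxicity" and sets this criterion: "The treatment will be considered safe if the grade 3+ treatment related toxicity rate is less than 20" percent. It describes that level as consistent with earlier SBRT studies of large tumors, which it says "report a grade 3+ toxicity rate of 5-25%, varying based on tumor location".

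Section 11.3 gives the only analysis method for toxicity: "Demographic and clinical characteristics including treatment toxicity will be summarized using descriptive statistics". Sections 11.2 and 11.4 attach a 95% interval of plus or minus 15 percentage points to local control alone.

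On the denominator, the Protocol Summary says "67 adult patients will be enrolled and treated, (with a goal of 47 evaluable patients", and the 47 refers to local control at 6 months. For toxicity, section 5.8 says "All patients enrolled on the study are evaluable for toxicity if they have received at least one fraction of radiation", and adds: "Participants who are consented but do not receive study treatment will be replaced".

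Section 11.6 monitors toxicity on a different footing: "We assume the TSAE rate is expected ~30% or less", with 40% or more not desired and a last boundary of 25 events in 67 patients.

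**The concern.** A statement that a treatment is considered safe is a decision, and a reader needs to know how often it would be reached when the true rate is too high. The plan gives neither an interval nor an error rate for it. The estimated rate from 67 patients has wide uncertainty, so a result just under 20% says little about whether the true rate is under 20%.

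Half of the primary conclusion is at stake. Followed exactly, the plan lets the report call the treatment safe, without qualification, when the data do not exclude rates well above the prior experience it cites.

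**Working it through.** **Inputs.** Criterion: rate below 20% (11.2). Toxicity denominator: 67, because all treated patients count and untreated ones are replaced (Protocol Summary, 5.8). Range of prior rates: 5-25% (11.2). Stopping boundary: table in 11.6.

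**The plan's own figure.** The largest half-width of the exact (Clopper-Pearson) 95% interval, over all possible results, is 15.10 points at n = 46 and 14.93 points at n = 47. So 47 is the smallest number that meets plus or minus 15 points. Then 47 / (1 - 0.30) = 67.1, in line with 67 enrolled. The local-control sizing reproduces. No comparable figure is given for toxicity.

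**The criterion as a count.** 13/67 = 19.4% and 14/67 = 20.9%, so a rate below 20% means 13 or fewer events.

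**Probability of meeting it.** With X binomial (67, p), P(X ≤ 13) is:

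| True rate p | P(13 or fewer of 67) |
|---|---|
| 10% | 0.994 |
| 15% | 0.879 |
| 20% | 0.524 |
| 25% | 0.181 |
| 30% | 0.035 |

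The result does not hinge on n being exactly 67. At n = 60, 64, 65, 66 and 67 the probability lies between 0.45 and 0.55 at a true 20%, and between 0.14 and 0.20 at 25%.

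**Interval at the limit.** For 13/67 the exact two-sided 95% interval is 10.8% to 30.9%.

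**Does the stopping boundary help?** I ran the 11.6 table patient by patient, taking the same event and the same p as in 11.2. The first row, as it reads in the text available, has 19 values for 20 columns, so I tried every position for the missing value. The probability of halting is 0.05-0.08 at a true 20% and 0.14-0.19 at 25%. The probability of finishing with 13 or fewer events and no halt is 0.51-0.52 at 20% and 0.17-0.18 at 25%, against 0.52 and 0.18 without the boundary.

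**When would 20% be excluded?** The upper limit of the exact two-sided 95% interval is 18.5% at 6/67 and 20.3% at 7/67, so 6 or fewer events are needed. P(X ≤ 6) is 0.950 at a true 5%, 0.490 at 10%, 0.107 at 15% and 0.012 at 20%.

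**The case against.** The trial is framed as estimation. Enrollment was set on clinical grounds rather than power, and toxicity is to be described. Any cut-off on a point estimate is met about half the time when the truth sits on the cut-off, so the 0.52 is partly built in. The protocol names neither 20% nor 25% as unacceptable; both lie inside its cited range, and the only rate called undesirable is 40% or more. The plan also does not use the word observed; that is a reading of it.

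Much of this stands. It argues against imposing a formal test, and it makes the 0.18 at 25% and 0.035 at 30% more informative than the 0.52. It does not remove the point. An estimation study should give an interval for each co-primary rate, and this one also announces a yes-or-no verdict. No other way of applying the criterion is described.

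Three stronger readings are tempting and are not supported.

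- **That 11.2 and 11.6 contradict each other** because 14 to 24 events would miss the 20% criterion without necessarily halting the trial. A stopping boundary is normally looser than a final criterion, and this one can halt much earlier (3 of 3, 20 of 50). The two sections may also count different events: treatment-related in 11.2; treatment-emergent and non-hematologic in 11.6, which elsewhere calls them related to Lattice SBRT.
- **That the boundary has one known halting probability at each true rate.** It depends on how the short first row is aligned, so only ranges can be given.
- **That safety should be claimable only at 7 or fewer events.** That limit comes from a one-sided 95% bound (18.7% at 7/67). It would be met only 19% of the time at a true 15%, and it disagrees with a reported two-sided interval, whose upper limit at 7/67 is 20.3%. Nothing in the plan calls for it.

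**Conclusion.** The concern holds as a gap between the verdict and the evidence that the plan requires for it. A treatment with a true grade 3+ related toxicity rate of 20% would be called safe with probability 0.52, and one at 25% with probability 0.18. A result of 13 of 67 is compatible with rates up to 30.9%. The stopping boundary lowers the two probabilities by no more than about 0.02.

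This rests on three assumptions: the criterion applies to the observed proportion, all 67 treated patients contribute a yes-or-no outcome, and, for the boundary calculation only, 11.6 counts the same events as 11.2. The trial remains interpretable, and the 20% figure itself is not shown to be wrong. The differing 20% and 30% rates need explaining, but on the text alone they are an unreconciled difference and not a proven contradiction.

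**What to change.** In 11.2 and 11.3:

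- Keep the 20% criterion and apply it to the number of patients actually treated.
- Report the exact two-sided 95% interval alongside the verdict.
- Print the probability of meeting the criterion: 0.88, 0.52, 0.18 and 0.035 at true rates of 15%, 20%, 25% and 30% (n = 67).
- If the observed rate is below 20% but the upper limit is 20% or more, word the conclusion as: *observed rate below 20%; a true rate of 20% or more is not excluded*. With 67 treated, this covers 7 to 13 events.
- State that a true rate of 20% or more is excluded only when the upper limit is below 20% (6 or fewer of 67).

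In 11.2 and 11.6, say whether the two sections count the same events, and reconcile the 20% criterion with the 30% acceptable rate. Check the first boundary row before quoting any halting probability.

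The cost is a few lines of text, with no change to sample size or treatment. The real price is a less favorable safety statement whenever the observed rate is below 20% but the interval includes 20%. That would be common: at a true 15%, the stronger statement would be available only about 11% of the time, and at a true 10% about 49%.

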As secondary endpoints, this study will evaluate patient reported outcomes through 12 months follow up. Comparisons of patient-reported outcomes such as pain in patients undergoing palliative radiotherapy are notoriously difficult. These can be impacted by the initial indication for palliative radiation (i.e. oligoprogression versus uncontrolled symptom), presence or absence of other tumors outside the target(s), subsequent therapies after treatment, and co-morbidities. This study will attempt to reduce this heterogeneity by studying the secondary endpoints within pre-specified subgroups. Additionally, this study will evaluate PROs using the reliable change index, which allows evaluation of the change of individual patient PROs of comparison to their own baseline.

The RCI utilizes the known retest reliability and standard deviation of a test to calculate the standard error of measurement and standard error of the difference between scores [Jacobson, 1992]. This value represents the level of change associated with statistically significant change from baseline. RCI is calculated as follows:

$$RCI = \frac{x_2 - x_1}{S_{diff}}$$

Where  $x_2 - x_1$  represents an individual's change between timepoints. This can also be reported as a difference in population mean.  $S_{diff}$ , the standard error of the difference between the two scores accounting for reliability of the test, is calculated as:

$$S_{diff} = \sqrt{2(S_E)^2}$$

$$S_E = s_1 \sqrt{1 - r_{xx}}$$

Where  $S_E$  is the standard error of measurement of the test,  $s_1$  is the standard deviation of the test results at the initial time point, and  $r_{xx}$  is the test-retest reliability of the measure. The test-retest reliabilities of PROMIS domains used in this study have been previously evaluated in patients with musculoskeletal conditions and range from 0.85-0.92 [Deyo, 2016].

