The RCI will be calculated for each individual patient for pain score, PRO-CTCAE, and each PROMIS domain between baseline and the 3, 6, and 12 month time points. In order for a change to be deemed statistically reliable at a 90% confidence interval, the Z-score of the RCI must be greater than 1.645. The 90% confidence interval is standard use in the literature when calculating RCI because it increases the sensitivity in detecting reliable change and defines a change which occurs in only 5% of healthy individuals in either direction [Stein, Gray, Schmitt, Hensel]. Changes that exceed this threshold in either direction are likely due to actual change rather than due to chance. Individual changes are reported as either significant increase, significant decrease, or no change.

Mean RCI for each time-point and domain will be calculated to determine significant change on a population level for each sub-group. The  $S_{diff}$  for each domain will be used to calculate a minimum important change at each time-point based on a 90% confidence interval. Lastly, the proportion of individuals in each histology cohort group whose RCI indicated significant increase, significant decrease, or no change in PRO scores will be reported.

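### The reliable change index has no reliability value for pain or PRO-CTCAE, and it breaks down for PRO-CTCAE items with zero or very small baseline spread

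*Combined protocol and SAP*

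**What the plan says.** Section 11.2 of the combined protocol and SAP introduces the index in general terms: "The RCI utilizes the known retest reliability and standard deviation of a test". It defines the index as the individual's change divided by S_diff, which is "the standard error of the difference between the two scores accounting for reliability of the test". S_diff is sqrt(2 × S_E²), with S_E = s1 × sqrt(1 − r). In that formula s1 "is the standard deviation of the test results at the initial time point".

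The only reliability figures are for one instrument: "The test-retest reliabilities of PROMIS domains used in this study have been previously evaluated in patients with musculoskeletal conditions and range from 0.85-0.92".

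The index is then applied to three instruments: "The RCI will be calculated for each individual patient for pain score, PRO-CTCAE, and each PROMIS domain", comparing baseline with 3, 6 and 12 months. For a change to count, "the Z-score of the RCI must be greater than 1.645", in either direction. The justification is that this threshold "defines a change which occurs in only 5% of healthy individuals in either direction". Three outputs follow: a label per patient (increase, decrease, no change), a mean index per sub-group, and a minimum important change derived from S_diff.

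Appendix D lists PRO-CTCAE as individual symptoms. Eleven are for everyone; the rest are for particular tumour sites (for example hiccups, fecal incontinence and hoarseness). No composite and no scoring range are given. Section 2.0 assigns the 11-point numeric pain scale to patients who have pain. Section 11.3 adds nothing on reliability or on the baseline SD.

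**The concern.** Two of the three instruments lack an input that the formula needs. Without r for pain and PRO-CTCAE, the cut-off cannot be computed from the plan, and a value chosen after the data are seen would decide which patients count as changed.

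A second problem is specific to PRO-CTCAE. The formula takes measurement error to be proportional to the spread of baseline scores. For a symptom that few patients have before treatment, that spread can be zero or very small, and the plan has no rule for this. The index then either cannot be calculated or calls any one-category movement reliable.

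PRO-CTCAE is the named measure for the patient-reported toxicity objective. What is at stake is how a secondary safety result is read: a label of significant change could reflect low baseline spread in an item rather than the size of the patient's worsening.

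**Working it through.** **Inputs from the documents:** the formulas and the 1.645 cut-off (Section 11.2); r = 0.85 to 0.92 for PROMIS (Section 11.2); at least 10 patients per cohort and 67 in total (Protocol Summary).

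**Assumptions:** r from 0.50 to 0.92 for pain and PRO-CTCAE; integer PRO-CTCAE scores of 0-4 per item; the baseline distributions shown below; a pain SD of 2.5. The documents give none of these.

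**The plan's own figure.** The two-sided 90% normal quantile is 1.645, and P(Z > 1.645) = 0.050 in each direction. The stated cut-off and the stated 5% agree.

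**Smallest flagged change.** Rearranging the plan's formulas, a change is flagged when it exceeds 1.645 × sqrt(2(1 − r)) × s1. A one-category change is therefore always flagged when s1 < 1 / (1.645 × sqrt(2(1 − r))).

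| r | Cut-off | One category always flagged if s1 is below |
|---|---|---|
| 0.50 | 1.645 × s1 | 0.61 |
| 0.60 | 1.471 × s1 | 0.68 |
| 0.70 | 1.274 × s1 | 0.79 |
| 0.85 | 0.901 × s1 | 1.11 |
| 0.92 | 0.658 × s1 | 1.52 |

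**Zero spread.** If every patient scores 0 at baseline, s1 = 0 and S_diff = 0. The index is 0/0 for a patient who does not change and a division by zero for one who does. If 5% of patients have the symptom (assumed), the chance that all score 0 is 0.95^10 = 60% in a group of 10, 0.95^17 = 42% in a group of 17 (about 67/4), and 0.95^67 = 3% in all 67. Site-specific items are completed only by the relevant site group, so the smaller figures for n are the relevant ones for them.

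**Small spread.** If m of n patients score g and the rest score 0, s1 = g × sqrt(m(n − m) / (n(n − 1))). For 1 of 10 at score 1, s1 = sqrt(9/90) = 0.316.

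| Baseline pattern | s1 | Cut-off, r = 0.70 | r = 0.85 | r = 0.92 |
|---|---|---|---|---|
| 1 of 10 at score 1 | 0.316 | 0.40 | 0.28 | 0.21 |
| 7 of 67 at score 1 | 0.308 | 0.39 | 0.28 | 0.20 |
| 7 of 67 at score 3 | 0.925 | 1.18 | 0.83 | 0.61 |
| 13 of 67 at score 4 | 1.594 | 2.03 | 1.44 | 1.05 |

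In the first two rows every one-category change is flagged. For 1 of 10 at score 1 this is still so at r = 0.60 (cut-off 1.471 × 0.316 = 0.47). In the third row the result turns on the unstated r: not flagged at 0.70, flagged at 0.85. In the fourth row a one-category change is not flagged at any of these values.

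**Same change, different label.** At r = 0.85, a one-category worsening is flagged on an item with the second pattern (cut-off 0.28) and not on an item with the fourth (cut-off 1.44).

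**Meaning of the 5%.** When the cut-off is below one category, the share of stable patients who are flagged is simply the share whose answer moves by one category or more. The factor 1.645 no longer controls it.

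**Pain.** At an assumed s1 of 2.5, the cut-off is 0.658 × 2.5 = 1.64 points for r = 0.92, 0.901 × 2.5 = 2.25 for r = 0.85, and 1.471 × 2.5 = 3.68 for r = 0.60. On a whole-point scale these mean changes of 2, 3 or 4 points.

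**The case against.** The strongest reply is that the floor argument can be pushed much further than the documents allow, and several parts of that reply stand.

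- A reader might infer that the index fails whenever most patients have no baseline symptom. It does not. With 7 of 67 at score 3, 90% are at zero, yet at r = 0.70 a one-category change is not flagged. The index is undefined only when s1 is exactly zero.
- A reader might infer that the planned proportions cannot be compared across the four cohorts. For a given item that holds only if s1 is computed per cohort. The plan does not say; a pooled s1 gives one cut-off per item.
- A reader might infer that all PRO-CTCAE results would be artefacts. The core list includes general pain, fatigue and insomnia, and no baseline distribution is given, so a floor cannot be presumed there.
- A reader might extend the floor argument to the pain scale. Section 2.0 restricts that scale to patients who have pain, so the argument does not reach it.
- Item-level 0-4 scoring is itself an assumption.

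It can also be said that counting every one-category worsening identifies the same worsened patients as the index does on a floor item. That is true. The difference is that a plain count applies one rule to every item and makes no claim of statistical reliability. A count of worsening alone would lose the improvement that Section 11.2 plans to report, so the replacement must keep it.

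None of this supplies the missing reliability values or a rule for zero or very small s1.

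**Conclusion.** The concern holds in a limited form. It is established from the documents alone that no reliability value is given for the pain score or PRO-CTCAE, that nothing covers a zero or very small baseline SD, and that the sample supplying s1 is not stated.

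For PRO-CTCAE items, the rule as written gives no result at s1 = 0 and labels every one-category change significant below a limit that depends on r (0.79 at r = 0.70; 1.11 at r = 0.85). This can arise for site-specific symptoms when nearly all patients score zero or the symptomatic minority is mild. For such items the 5% interpretation does not hold, and equal changes can be labelled differently between items, and between cohorts if s1 is taken per cohort. How often this will happen cannot be determined, because it rests on assumed scoring, reliability and baseline distributions.

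For pain the defect is only the unstated r, which moves the cut-off from 1.6 to 3.7 points over r = 0.92 to 0.60 at an assumed SD of 2.5.

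Only secondary endpoints are affected. The co-primary endpoints and the sample size are not. The change should be made before analysis.

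**What to change.** Amend Section 11.2 as follows.

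- **PROMIS:** keep the index, and state that s1 is pooled over all patients.
- **PRO-CTCAE:** drop the index. State the item scoring. For each item and time point, report the proportions of patients worse than, better than and unchanged from their own baseline score, and the proportion reaching a high score (3 or more, if scoring is 0-4) that is worse than baseline. Do not call these changes significant. State the denominator, since Section 2.0 assigns PRO-CTCAE to patients without pain and Appendix D to all patients.
- **Pain scale:** before analysis, fix one reliability value with its source and the resulting whole-point change, the same for all cohorts.

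The cost is analysis wording only, with no new data collection. The downside is that the three instruments no longer share one summary metric and the PRO-CTCAE results become purely descriptive. The comparison of each patient with their own baseline, which is the plan's stated reason for using the index, is preserved.
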